9.2 Visit description

General information

Timing of the visits

If not stated otherwise, the measures listed in the following sections will be performed by or under the supervision of a study site investigator.

There will be 8 scheduled study visits: screening visit (Visit 1), baseline visit (Visit 2), 5 visits during the treatment phase (Visit 3 to 7) and the end-of-treatment visit (EOT, Visit 8). The end-of-study visit (EOS) is a phone contact at 3 weeks after the EOT (all subjects).

In addition, there will be up to 2 follow-up contacts for post-treatment pregnancy tracking. 3-month follow-up contact is for subjects who prematurely discontinued study treatment unless the reason for discontinuation is “pregnancy”, “death”, or “withdrawal by subject” where the subject has withdrawn main consent during study conduct and wishes to stop future contact with the site. For subjects that had withdrawn consent during study, but consented to post study participation follow-up, will be contacted. If subjects could not be contacted at 3 months, they will be considered “Lost to Follow-up” for post-study pregnancy tracking. 12-month contact is for subjects that prematurely discontinued treatment due to ‘Wish for pregnancy’. If a subject was not pregnant at 3-month contact but subject no longer wished to become pregnant, a 12-month contact is not required. If subject was “Lost to Follow-up” at 3 months, a 12-month contact is required. For details, see Section 9.4.1.2.

The screening period can start when the subject has had the Mirena in place for 4 years and 6 months. Screening period is up to 6 months. Screening activities should be completed within 60 days after signing the informed consent. The baseline visit (Visit 2) should take place 14 to 0 days before the end of Year 5 of Mirena use.

The timing of the visits is based on the date of the baseline visit. Treatment period starts at the baseline visit (Visit 2, defined as Study Day 1).

The following visit windows are allowed:

- Visits 3 to 7 (during treatment) should be performed ± 2 weeks of the scheduled day.
- Visit 8 (EOT) should be performed at the earliest 2 weeks before the scheduled day and not later.
- Follow-up contact (EOS) should take place 3 weeks after the EOT (-3 day window allowed).

Unscheduled visits

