9.6.3.8 Presence of Mirena removal threads

This section was changed in Amendment 1, see Section 15.1.1.22.

The presence of the removal threads will be checked at each study visit and recorded in the eCRF.

The investigator will perform pelvic examinations at each study visit to verify the presence of the Mirena removal threads in the appropriate location in the cervical os. If the presence of the removal threads cannot be verified, transvaginal ultrasound (TVUS) is to be performed to verify that the Mirena is in the appropriate intrauterine location and to exclude expulsion or perforation. The subject should be instructed to periodically check the threads by feeling for the threads at the top of the vaginal canal and if, at any time of the study, a subject suspects that the Mirena may have been expelled, she should contact the investigator and the investigator should assess the need for an unscheduled visit to evaluate the location of the Mirena. The subject should be instructed to use non-hormonal back-up method of contraception until it is confirmed that the Mirena is in the proper location.

Subject is **in compliance** with Mirena when:

- Threads are visible, or,
- Threads are not visible (or not checked) but TVUS performed to localize the Mirena shows Mirena to be “In situ” or “Displaced intrauterine”.

Subject is **non-compliant** with Mirena when:

- Threads are not visible, and,
- TVUS performed to localize Mirena shows that the IUS is “Partially or totally expelled into vagina or cervical canal”, “Cervical perforation”, “Myometrial perforation”, “Localization in the peritoneal cavity”, or “Absent”.
- Threads are visible, but TVUS is performed for other reason(s) and Mirena localization is recorded as “Partially or totally expelled into vagina or cervical canal”, “Cervical perforation”, “Myometrial perforation”, “Localization in the peritoneal cavity”.

Non-compliance with Mirena necessitates discontinuation of the subject from the study. In case the IUS is partially expelled, it needs to be removed. In case perforation has occurred, the IUS needs to be removed using appropriate procedures.

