4.7 Data Rules

Start date of 'treatment period'

The date of baseline visit will be considered the start date of the 'treatment period', i.e. study day 1.

Start date of study drug administration, i.e. start date of 'extension treatment period'

Day 1 of Year 6 of Mirena use will be considered the start date of study drug administration.

Date Mirena last known in situ

The 'date Mirena last known in situ' is referred to in Integrated Protocol Section 10.3.2.1 and Integrated Protocol Table 10-1 and is needed to calculate the crude exposure time for PI calculation for subjects who were lost to follow-up (e.g. because the woman withdrew consent, was lost to follow-up, or died) and for ongoing subjects (during the analyses after Year 6 and Year 7).

The 'date Mirena last known in situ' will be the latest date when the subject was found to be compliant with Mirena, before the first occurrence of non-compliance (if any).

Compliance/non-compliance is described in Section 6.1.3.5 and Integrated Protocol Section 9.6.3.8.

Therefore, the 'date Mirena last known in situ' will be the latest of the following:

- Last date (before the first occurrence of non-compliance, if any) when Mirena threads were visible
- Last date (before the first occurrence of non-compliance, if any) when Mirena location was found to be "In situ" or "Displaced, intrauterine"

If any of these dates is missing or partial, it will be imputed individually as described in Section 4.3.

Stop date of study drug administration

If the Mirena was totally expelled or removed during the study, the stop date of study drug administration will be the date of Mirena expulsion or removal.

If the Mirena was not totally expelled or removed during the study (e.g. because the woman withdrew consent, was lost to follow-up, or died), the stop date of study drug administration will be the 'date Mirena last known in situ'.

For ongoing subjects (during the analyses after Year 6 and Year 7), the stop date of study drug administration will be the 'date Mirena last known in situ'.

Woman-years

One woman-year will comprise 365 days of study treatment exposure, unless otherwise stated.

Treatment-emergent AEs

The onset date of AEs will be used to distinguish between treatment-emergent and pre-treatment AEs. If an event occurred on Day 1 of Year 6 of Mirena use or later, it will be considered as treatment-emergent AE. Otherwise, it will be considered as pre-treatment AE.

AEs in 6th / 7th / 8th year

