6.1.3.3 Expulsion rates

As described in Integrated Protocol Section 9.6.3.9, total or partial expulsion of the Mirena must be reported as an AE. Furthermore, expulsions must be recorded on the eCRF page “Intrauterine System Removal” as “Totally expelled” and “Partially expelled and removed”, respectively.

The number of subjects with expulsion (at least partial, or total) of the Mirena during the ‘extension treatment period’ (starting at Day 1 Year 6) will be summarized in a frequency table, overall and by parity, BMI, race and ethnicity.

The time from Day 1 Year 6 to expulsion will be analyzed using the Kaplan-Meier estimator. If no expulsion occurred in a subject, this will be considered a censored observation and the stop date of study drug administration (as defined in Section 4.7) will be used as censoring date.

The estimated proportion of subjects with expulsion of the Mirena will be reported for the time points 6 months (5.5 years of Mirena use), 12 months (6 years of Mirena use), 18 months (6.5 years of Mirena use), 24 months (7 years of Mirena use), 30 months (7.5 years of Mirena use), and 36 months (8 years of Mirena use). The cumulative proportion will be estimated.

All subjects with partial or total expulsion of the Mirena will be listed. The listing will contain the parity status and the time in days after Day 1 Year 6 when the expulsion was discovered.

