6.1.3.5 Compliance

The definition of compliance with Mirena is given in Integrated Protocol Section 9.6.3.8.

The number of subjects compliant and non-compliant, respectively, during the ‘extension treatment period’ (starting at Day 1 Year 6) will be summarized over time in frequency tables, overall and by parity status (no birth vs. at least one birth).

The time from Day 1 Year 6 to (first) non-compliance will be analyzed using the Kaplan-Meier estimator. If no non-compliance occurred in a subject, this will be considered a censored observation and the stop date of study drug administration (as defined in Section 4.7) will be used as censoring date.

The estimated proportion of subjects who are compliant will be reported for the time points 6 months (5.5 years of Mirena use), 12 months (6 years of Mirena use), 18 months (6.5 years of Mirena use), 24 months (7 years of Mirena use), 30 months (7.5 years of Mirena use), and 36 months (8 years of Mirena use). The cumulative proportion will be estimated as well.

The number of subjects in each sub-category will be summarized over time in frequency tables, overall and by parity, as follows:

- Compliant with Mirena
 - Threads visible
 - Threads not visible and transvaginal ultrasound (TVUS) performed => location of Mirena:
 - In situ
 - Displaced, intrauterine
- Non-compliant with Mirena
 - Threads not visible and TVUS performed => location of Mirena:
 - Partially or totally expelled into vagina or cervical canal
 - Cervical perforation
 - Myometrial perforation
 - Migration to the peritoneal cavity

- Absent
- Other
- Threads visible and TVUS performed => location of Mirena:
 - Partially or totally expelled into vagina or cervical canal
 - Cervical perforation
 - Myometrial perforation
 - Migration to the peritoneal cavity
 - Other

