6.4.2.1 Perforation rates

As described in Integrated Protocol Section 9.6.3.9, perforation by the Mirena must be reported as an SAE. If a perforation is diagnosed, Mirena must be removed and the subject must discontinue study treatment and the study.

Perforations will be identified from the AEs recorded on the eCRF coded by MedDRA as one of the following:

- Preferred Term “Uterine perforation”
- Preferred Term “Embedded Device”,
- Preferred Term “Fallopian tube perforation”,
- Lowest Level Term “Extrauterine intra-abdominal localisation of IUD”,
- Lowest Level Term “Extrauterine intra-abdominal localization of IUD”,

- Lowest Level Term “IUD migration”,
- Lowest Level Term “Device migration”,
- Lowest Level Term “Device dislocation into abdominal cavity”.

The number of subjects with perforation by the Mirena during the ‘extension treatment period’ (starting at Day 1 Year 6) will be summarized in a frequency table, overall and by parity.

In addition, the time from Day 1 Year 6 to perforation will be analyzed using the Kaplan-Meier estimator. If no perforation occurred in a subject, this is considered a censored observation and the stop date of study drug administration (as defined in Section 4.7) will be used as censoring date.

The estimated proportion of subjects with perforation of the Mirena will be reported for the time points 6 months (5.5 years of Mirena use), 12 months (6 years of Mirena use), 18 months (6.5 years of Mirena use), 24 months (7 years of Mirena use), 30 months (7.5 years of Mirena use), and 36 months (8 years of Mirena use). The cumulative proportion will be estimated as well.

All subjects with perforation by the Mirena will be listed. The listing will contain the parity status as well as the duration from last birth or induced/spontaneous abortion to insertion and the time in days after Day 1 Year 6 when the perforation was discovered.

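### The 36-month Kaplan-Meier rates for non-compliance, perforation and (if dated by discovery) expulsion over-weight events found at Visit 8, because event-free completers are censored at that same visit

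*SAP*

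**What the plan says.** Three device curves share one censoring rule, with time running from Day 1 of Year 6.

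- Expulsion, SAP 6.1.3.3: "If no expulsion occurred in a subject, this will be considered a censored observation and the stop date of study drug administration" is the censoring date.
- Non-compliance, SAP 6.1.3.5: "The time from Day 1 Year 6 to (first) non-compliance will be analyzed using the Kaplan-Meier estimator", and "If no non-compliance occurred in a subject, this will be considered a censored observation and the stop date of study drug administration" again supplies the date.
- Perforation, SAP 6.4.2.1: "the time from Day 1 Year 6 to perforation will be analyzed using the Kaplan-Meier estimator", with "If no perforation occurred in a subject, this is considered a censored observation and the stop date of study drug administration" in the same role.

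SAP 4.7 defines that date. For a woman whose device is expelled or removed, "the stop date of study drug administration will be the date of Mirena expulsion or removal". For women still in the study at the Year 6 and Year 7 analyses it is the last date the device was confirmed in place, normally the Visit 4 or Visit 6 check. All three curves are read at six-month steps up to 36 months.

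On timing, Protocol 9.6.3.8 says "The presence of the removal threads will be checked at each study visit and recorded in the eCRF". Protocol 9.2.9 places both that check and the removal at Visit 8. Protocol 9.2 times visits from baseline, which falls 0 to 14 days before the end of Year 5, and adds that "Visit 8 (EOT) should be performed at the earliest 2 weeks before the scheduled day and not later". Visits 3 to 7 may fall up to two weeks either side of schedule.

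The expulsion and perforation listings give the day of discovery. The SAP does not say which date the expulsion curve uses, and the pregnancy listing in SAP 6.2.1 shows that an estimated expulsion date may also exist.

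**The concern.** Kaplan-Meier divides each event by the women still under observation on that day. This is sound when leaving observation is unrelated to when events are found. Here the final examination both finds the event and ends observation. All completers receive that examination, so the natural denominator for an event found there is all completers. The rule instead uses only those whose Visit 8 date has not yet come, and that number runs down towards zero just before the read-out.

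The size of the jump therefore depends on how early or late in the window a woman happened to be seen. The convention that events precede censoring on ties protects only women seen on the same day.

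Protocol 10.3.1.2 names expulsion and perforation rates as safety variables, and the study is meant to support use up to 8 years. The 36-month value is the one readers will look for, and on average it would overstate harm.

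**Working it through.** **Inputs.** The target is 200 completers (Protocol 10.4). Baseline lead *d* is 0-14 days and Visit 8 earliness *w* is 0-14 days (Protocol 9.2). With 36 months taken as 1095 days, removal falls on day 1095 − *d* − *w*, that is days 1067 to 1095. The documents give no device event rates, no spread of visits within windows and no late share; all of these are assumed below.

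**Calibration to the plan's own figure.** Reading the 15% dropout as yearly: 350 × (1 + 0.85 + 0.85²) × 0.925 = 832.8 woman-years, against 832 stated. This reading leaves 350 × 0.85³ ≈ 215 completers, close to the 200 target.

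**Weight of one Visit 8 event.** If *Y* women remain unseen, the event adds 1/*Y* instead of 1/200. With 100 unseen it adds 1.0% instead of 0.5% (2-fold); with 10 unseen, 10% (20-fold). If visits are spread evenly over *m* days, the mean over-weighting is 1 + 1/2 + … + 1/*m*: 1.0 for one day, 2.7 for 8 days, 3.3 for 15 days.

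Simulation with 200 completers, all in window:

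| Spread of Visit 8 dates | Mean fold |
|---|---|
| 15-day window only, or baseline lead only | 3.3 |
| Lead 0-3 and window 0-3 days | 3.0 |
| Lead 0-7 and window 0-7 days | about 4.0-4.5 |
| Lead 0-14 and window 0-14 days | about 4.6-5.3 |

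For a single event over the full lead and window the median is about 1.9, and the 5th to 95th percentiles run from about 1.0 to 15.

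**Late removals.** If a share *p* of completers is still at risk at the read-out, the expected weight is about −ln(*p*). For *p* = 5%, 10% and 20% this is 3.0, 2.3 and 1.6. Simulation with late removals 1-28 days after day 1095, read at day 1095, gives about 2.8, 2.2 and 1.5.

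**Whole 36-month rate.** Simulation of 350 women with 15% yearly dropout, for 0.5% risk per six months: true 36-month rate 1 − 0.995⁶ = 2.96%.

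| Visit timing | No event noticed between visits | Half noticed between visits |
|---|---|---|
| Full window, 0-14 day lead | 5.15% (1.74-fold) | 4.13% (1.39) |
| Full window, no lead | 4.12% (1.39) | 3.62% (1.22) |
| Within 3 days of schedule, 0-14 day lead | 4.53% (1.53) | 3.62% (1.22) |
| On schedule, 0-14 day lead | 4.12% (1.39) | 3.56% (1.20) |

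At 0.25% and 1% per six months, with full window and lead, the ratios are 1.34 to 1.64. Median ratios over all scenarios are 1.02 to 1.26. The whole rate moves less than the Visit 8 increment because only about 6-13% of events are found at Visit 8.

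**Interim read-outs.** With full window and lead, about 75% of Visit 4 dates fall by day 365, so events found there get a weight of about −ln(0.25) = 1.39. With no lead about half do, and −ln(0.5) = 0.69, which is below 1. Whole-rate mean ratios:

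| Visit timing | 12 months | 24 months |
|---|---|---|
| Full window, 0-14 day lead | 1.06-1.21 | 1.04-1.12 |
| Full window, no lead | 0.88-0.93 | 0.95-1.00 |
| At or near schedule, 0-14 day lead | 1.4-2.2 | 1.2-1.7 |

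**After the fix.** Placing all last-visit events and censoring on day 365, 730 or 1095 gives mean ratios of 0.96-1.04 in every scenario.

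**The case against.** The strongest case against has four parts.

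- **Event dates.** Only non-compliance is clearly dated to a visit. Perforations come from coded adverse events. Women check their own threads, and a woman can herself confirm a total expulsion. SAP 4.3 has rules for partial event dates, which suggests that not every date is a visit date. This stands: events noticed between visits are unaffected, and expulsion is affected only if discovery dates are used.
- **Adherence.** The high mean weights come from the last few women at risk. The SAP itself expects some departures: adverse events at the start of Year 9, baselines after Day 1 of Year 6, and Covid-affected visits. This also stands, and it is why the late-removal range is given.
- **Consequences.** No success criterion uses these curves. Frequency tables are planned for all three, and day-of-discovery listings for expulsion and perforation. At 36 months the mean bias is against the product. This lowers the severity. It does not repair the estimate, because crude frequencies do not account for dropout.
- **Scope.** A reader might infer three stronger things that the documents do not support:
  - That the 6- and 7-year rates are inflated as well. The windows of Visits 4 and 6 straddle the time point, so the direction depends on actual visit timing. The final-analysis curve does not censor continuing women there at all.
  - That the reported 36-month rate is wrong by 3- to 5-fold. That figure is the mean for the Visit 8 increment alone.
  - That the pregnancy and discontinuation curves share the inflation and should stop at day 1067, the earliest in-window removal. Pregnancy is dated by conception, and a completer's Visit 8 is not a premature discontinuation. Stopping the pregnancy curve there would drop late conceptions and so understate failure.

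**Conclusion.** The point holds for the 36-month value in the final analysis: for non-compliance, for perforation where it is dated by discovery, and for expulsion if the curve uses discovery dates. An event dated to Visit 8 is over-weighted about 3- to 5-fold on average, typically about 2-fold, if removals stay in window with the 0-14 day baseline lead. The mean is about 1.5- to 3-fold if 5-20% of removals are late. The whole rate then rises about 1.2- to 1.7-fold on average in the in-window scenarios, and not at all if no event is dated to Visit 8. At 12 and 24 months of the interim analyses the bias can go either way.

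The mechanism follows from the text. The sizes rest on assumed event rates, visit spread, late share and share of events noticed between visits. Severity is moderate: named safety variables are affected, but no decision rule depends on them.

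**What to change.** In SAP 6.1.3.3, 6.1.3.5 and 6.4.2.1:

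1. Assign events found at the last scheduled visit of each analysis, and censoring at that visit, to the nominal visit day (month 12, 24 or 36), so that all women examined there form the risk set.
2. Keep actual dates for events noticed between visits.
3. State that the event date is the date of discovery.
4. Show the number at risk at each reported time point.

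Leave the pregnancy and discontinuation curves at full length and add numbers at risk to them too.

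The cost is SAP wording and programming; no new data are needed. There is precedent: SAP v4.0 changed the censoring of completers for the discontinuation curve. The downside is a slightly coarser time scale for events found at visits.

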6.1.3.4 Discontinuation rates

The number of subjects who discontinued study treatment prematurely during the ‘extension treatment period’ (starting at Day 1 Year 6) as well as the primary/ underlying reason for premature discontinuation will be summarized in a frequency table, overall and by parity.

The time from Day 1 Year 6 to premature discontinuation will be analyzed using the Kaplan-Meier estimator. If the subject completed the study treatment period, this will be considered a censored observation and the date of Visit 8 / Month 36 will be used as censoring date. If no premature discontinuation of study treatment occurred because the subject is still continuing

in the study, this will be considered a censored observation and the date of the last visit during the treatment period will be used as censoring date.

The estimated proportion of subjects who discontinued study treatment prematurely will be reported for the time points 6 months (5.5 years of Mirena use), 12 months (6 years of Mirena use), 18 months (6.5 years of Mirena use), 24 months (7 years of Mirena use), 30 months (7.5 years of Mirena use), and 36 months (8 years of Mirena use). The cumulative proportion will be estimated.

6.1.3.5 Compliance

The definition of compliance with Mirena is given in Integrated Protocol Section 9.6.3.8.

The number of subjects compliant and non-compliant, respectively, during the ‘extension treatment period’ (starting at Day 1 Year 6) will be summarized over time in frequency tables, overall and by parity status (no birth vs. at least one birth).

The time from Day 1 Year 6 to (first) non-compliance will be analyzed using the Kaplan-Meier estimator. If no non-compliance occurred in a subject, this will be considered a censored observation and the stop date of study drug administration (as defined in Section 4.7) will be used as censoring date.

The estimated proportion of subjects who are compliant will be reported for the time points 6 months (5.5 years of Mirena use), 12 months (6 years of Mirena use), 18 months (6.5 years of Mirena use), 24 months (7 years of Mirena use), 30 months (7.5 years of Mirena use), and 36 months (8 years of Mirena use). The cumulative proportion will be estimated as well.

The number of subjects in each sub-category will be summarized over time in frequency tables, overall and by parity, as follows:

- Compliant with Mirena
 - Threads visible
 - Threads not visible and transvaginal ultrasound (TVUS) performed => location of Mirena:
 - In situ
 - Displaced, intrauterine
- Non-compliant with Mirena
 - Threads not visible and TVUS performed => location of Mirena:
 - Partially or totally expelled into vagina or cervical canal
 - Cervical perforation
 - Myometrial perforation
 - Migration to the peritoneal cavity

- Absent
- Other
- Threads visible and TVUS performed => location of Mirena:
 - Partially or totally expelled into vagina or cervical canal
 - Cervical perforation
 - Myometrial perforation
 - Migration to the peritoneal cavity
 - Other

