9.6.3.9 Expulsion of Mirena

Total or partial expulsion of the Mirena **will be reported as an AE or SAE, as appropriate** (i.e. meets the criteria for an SAE as specified in Section 9.6.1.1).

Total expulsion is confirmed if Mirena is observed in the vagina, it is not shown in the uterine cavity by ultrasound, and/or the subject confirms that the system was expelled. If, upon pelvic examination, the removal thread(s) cannot be seen, expulsion should be considered and an ultrasound must be performed. Possibilities of cervical or uterine perforations may be

excluded by ultrasound, x-ray or hysteroscopy before making a final diagnosis of total expulsion.

Partial expulsion is diagnosed if the Mirena can be partially seen in the vagina or is displaced in the cervical canal. If Mirena is partially expelled, it must be removed.

Upon total or partial expulsion of Mirena, the subject must discontinue study treatment and the study.

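### A partial expulsion seen on examination, with threads visible and no ultrasound, is scored as compliant, so the compliance curve can miss events that the expulsion analysis counts

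*SAP*

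**What the plan says.** Protocol 9.6.3.8 defines compliance in two ways: the threads are visible, or they are not visible (or not checked) but TVUS shows the device in place or displaced within the uterus. Non-compliance also has two routes. One is threads not visible with a TVUS finding of expulsion, perforation or absence. The other reads "Threads are visible, but TVUS is performed for other reason(s) and Mirena localization is recorded as" one of the listed expulsion or perforation locations. Both routes need a TVUS result. The duty to scan is tied to the threads: "If the presence of the removal threads cannot be verified, transvaginal ultrasound (TVUS) is to be performed".

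Protocol 9.6.3.9 sets a separate test for the event itself: "Partial expulsion is diagnosed if the Mirena can be partially seen in the vagina or is displaced in the cervical canal". It requires no ultrasound for that diagnosis. After a partial or total expulsion the woman must stop treatment and leave the study.

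SAP 6.1.3.5 takes over the protocol definition ("The definition of compliance with Mirena is given in Integrated Protocol Section 9.6.3.8"). Its only non-compliant category for a woman with visible threads is the one with TVUS performed. For time to first non-compliance it adds: "If no non-compliance occurred in a subject, this will be considered a censored observation". The censoring date is the stop date of study drug, which SAP 4.7 sets to the date of expulsion or removal.

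The expulsion analysis in SAP 6.1.3.3 draws on other records. Expulsions are reported as adverse events, and "expulsions must be recorded on the eCRF page “Intrauterine System Removal” as “Totally expelled” and “Partially expelled and removed”, respectively".

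**The concern.** Two sections of the protocol use different evidence for the same event, and the SAP builds a separate time-to-event analysis on each. A partial expulsion seen with threads visible and no scan meets the test in 9.6.3.9. It leads to removal and discontinuation and is an event in SAP 6.1.3.3. Under 9.6.3.8 and SAP 6.1.3.5 the same woman never becomes non-compliant.

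She is then treated as an uninformative censored observation on the day her device is taken out because it was no longer in place. Estimated non-compliance could fall below estimated expulsion in the same women, although expulsion is one of the listed forms of non-compliance. The study report would have to explain that discrepancy, and the error can only make compliance look better.

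**Working it through.** **The rules applied to one woman.** Partial expulsion is seen at a visit, threads are visible, no TVUS is done, and the device is removed.

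1. Protocol 9.6.3.9: partial expulsion is diagnosed and she must discontinue.
2. Protocol 9.6.3.8, compliance: visible threads are sufficient, so she is compliant.
3. Protocol 9.6.3.8, non-compliance: both routes need a TVUS location and she has none, so neither applies.
4. SAP 6.1.3.5: no non-compliance event, so she is censored at the stop date.
5. SAP 4.7: the stop date is her removal date.
6. SAP 6.1.3.3: she is an expulsion event.

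No other SAP text closes the gap. SAP 4.3 lists dates of expulsion, perforation and non-compliance side by side. SAP 6.2.1 names partial expulsion and first non-compliance as alternatives. A programmer therefore cannot take one to imply the other.

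**Size.** The documents give no compliance rate, no expulsion rate and no share of expulsions found without TVUS, so there is no stated figure to reproduce. The following is an illustration only.

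Inputs:
- e = 3-year expulsion probability (assumed: 1%, 3%, 5%)
- f = share of expulsions found with threads visible and no TVUS (assumed: 0 to 1)
- constant hazard, with other causes of non-compliance set to zero (assumed)
- 360 women (SAP 3)
- 15% dropout (Protocol 10.4), read as yearly. The protocol's own exposure supports this reading: 350 × 0.925 × (1 + 0.85 + 0.7225) = 832.8, against the stated 832 woman-years.

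Formulas:
- 36-month compliance if every expulsion counts: 1 − e
- 36-month compliance under the rule as written: (1 − e)^(1 − f)
- expected expulsions: 360 × h/(h + λ) × [1 − exp(−3(h + λ))], with h = −ln(1 − e)/3 and λ = −ln(0.85) = 0.1625

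Example with e = 3%, f = 0.5: 0.97^0.5 = 98.49%, against 97.00%, an excess of 1.49 points. Non-compliance from expulsion would read 1.51% beside an expulsion estimate of 3.00%.

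36-month compliance under the rule (%):

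| e | f = 0 | f = 0.25 | f = 0.5 | f = 0.75 | f = 1 | Expected expulsions | Missed at f = 0.5 |
|---|---|---|---|---|---|---|---|
| 1% | 99.00 | 99.25 | 99.50 | 99.75 | 100 | 2.9 | 1.4 |
| 3% | 97.00 | 97.74 | 98.49 | 99.24 | 100 | 8.6 | 4.3 |
| 5% | 95.00 | 96.23 | 97.47 | 98.73 | 100 | 14.3 | 7.1 |

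The f = 0 column is also the value after the fix. The excess is roughly e × f, so it runs from zero to e.

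**The case against.** The strongest reply is that the gap is narrow and touches nothing important. Most of this stands.

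- A reader might infer that expulsions in general are censored as compliant. The documents do not support that. When threads cannot be verified, TVUS is mandatory under 9.6.3.8, and 9.6.3.9 repeats the duty: "the removal thread(s) cannot be seen, expulsion should be considered and an ultrasound must be performed". Those cases then fall into the expelled or absent categories and count as non-compliant. The thread check also looks for threads in their proper place at the cervical os, so a device lying in the vagina may well fail it and be scanned.
- A reader might also infer that threads usually stay visible in a partial expulsion. Neither document says so. They show only that the combination was foreseen, because 9.6.3.8 has a branch for it.
- Section 9.6.3.9 does not exclude ultrasound, and it names no method for detecting displacement in the cervical canal. The accurate statement is that ultrasound is not required.
- Compliance is not among the efficacy, safety or other variables listed in Protocol 10.3.1. Expulsion and discontinuation have their own Kaplan-Meier analyses at the same six time points (SAP 6.1.3.3 and 6.1.3.4), and every expulsion is listed.
- SAP 4.7 uses thread visibility for the date the device was last known in situ. That date does not enter the stop date of a woman whose removal is recorded, so amending 4.7 would change almost nothing here.

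The reply does not remove the misclassification. The branch for visible threads shows that the authors recognised this woman, yet it counts her only if a scan happened to be done for another reason.

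**Conclusion.** The concern holds within limits. The rule as written gives a wrong classification for one type of case: partial expulsion found with threads visible and no TVUS. If at least one such case occurs, the compliance estimate is too high. If none occurs, nothing changes. The excess lies between zero and the full expulsion probability. The figures of 0.5, 1.5 and 2.5 points at f = 0.5 rest wholly on assumed values of e and f, so they should not be read as a forecast, and a statement that non-compliance is halved would merely restate the choice of f.

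A reader might infer that the expulsion rate or the Pearl Index is biased. The expulsion rate uses the adverse event and removal-page records and does not depend on the compliance rule. Pearl Index exposure in SAP Table 6–1 ends at discovery of a total expulsion or at removal, so it is unaffected for women with one of those dates recorded. The consequence is confined to one descriptive summary and its possible inconsistency with the expulsion table.

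**What to change.** Add one rule to SAP 6.1.3.5: any partial or total expulsion recorded as an adverse event or on the Intrauterine System Removal page counts as non-compliance from its date of discovery, whatever the thread finding and whether or not TVUS was done. The SAP 4.3 imputation for incomplete expulsion dates can be used unchanged. The rule would also classify an expulsion with threads not visible where the required scan was not done, which at present fits no category.

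Protocol 9.6.3.8 and 9.6.3.9 should be reconciled, because they apply different evidence to the same event. The SAP rule needs no change to clinical management, since discontinuation after expulsion is already required.

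The cost is a sentence and a programming line on data already collected. Reported compliance may become slightly less favourable. The 6- and 7-year values in the final analysis may also differ from those produced at the Year 6 and Year 7 analyses, which a table footnote can explain.
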